9. RESEARCH DESIGN AND METHODS

This investigation will be a randomized, subject-masked, active-controlled parallel-arm, human subjects clinical trial. Of note, we will be using standard-of-care local anesthetic under an FDA-approved purpose and do not plan to research a possible change of indication or use of these medications as part of this research project. The treatments in both groups are currently used at our institution and there is true clinical equipoise at this time. The only difference in treatment between subjects who enroll versus those not enrolled in this study will be those who enroll will have the decision between which anatomic block location determined randomly, as opposed to the physician simply choosing him/herself.

Enrollment. Consenting adults undergoing breast surgery with a planned single-injection regional analgesic will be offered enrollment. Patients undergoing breast surgery with a planned perineural catheter regional analgesic will be excluded. Study inclusion will be proposed to eligible patients prior to surgery. If a patient desires study participation, written, informed consent will be obtained using a current UCSD IRB-approved ICF. Selection for inclusion will not be based on gender, race, or socioeconomic status. The study population of interest includes men and women of all races and socioeconomic status. Inclusion and exclusion criteria are listed in section #9 below.

Preoperative Procedures. Following written, informed consent, we will collect baseline anthropomorphic information (e.g., age, sex, height, and weight). All subjects will have a peripheral intravenous (IV) catheter inserted, standard noninvasive monitors applied, supplemental oxygen administered via a nasal cannula or face mask, and placed in the sitting position. Midazolam and fentanyl (IV) will be titrated for patient comfort, while ensuring that patients remain responsive to verbal cues. Both possible block locations will be viewed with ultrasound. If one or both of the locations is unacceptable for block placement in the clinician's opinion, the subject will not be randomized and will not proceed further with the study.

Subjects will then be randomized using a computer-generated list and opaque, sealed envelopes to

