one of two treatment groups: (blocks of 4, stratified for unilateral vs. bilateral surgery): (1) erector spinae plane or (2) paravertebral block. All blocks will be placed by a regional anesthesia fellow or resident under the direct supervision and guidance of a regional anesthesia attending (or by the attending him/herself).

The area of needle insertion will be cleaned with chlorhexidine gluconate and isopropyl alcohol. All blocks will be placed using standard UCSD ultrasound-guided techniques as previously described.^{4,5}

Ropivacaine 0.5% (with epinephrine 1:200,000-400,000) will be administered via the needle into the target plane. For erector spinae plane blocks, this will be at the T3 level for surgery involving the axilla and the T4 level for surgery not involving the axilla (20 mL of local anesthetic for unilateral surgery; 16 mL of local anesthetic each side for bilateral surgery). For PVBs without axillary work, this will be at the T3 and T5 levels. For PVBs with axillary work, this will be at the T2 and T4 levels. For unilateral PVBs, 10 mL of local anesthetic will be injected per level. For bilateral PVBs, 8 mL of local anesthetic will be injected per level.

Single-injection blocks will be considered successful if, within 30 minutes, the subject experiences decreased sensation to cold temperature with an alcohol pad over the approximate level of the ipsilateral 4th thoracic dermatome. Misplaced blocks will be replaced successfully, or the patient excluded from further study participation. For subjects undergoing bilateral surgical procedures, a block using the same protocol will be administered on the contralateral side.

Intraoperatively, all subjects will receive a general anesthetic using inhaled and intravenous anesthetic and oxygen. Intravenous fentanyl will be administered for cardiovascular responsiveness to noxious stimuli at the discretion of the anesthesia provider.

Postop: Subjects will be discharged with a prescription for oxycodone 5 mg tablets for supplementary analgesia and instructed to record the time at which they take their first opioid tablet as well as the time at which they believe the block starts to wear off.

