Outcome measurements (end points). Pain scores will be recorded using the NRS. Within the recovery room, pain scores, opioid requirements, and antiemetic administration will be recorded by nursing staff masked to treatment group. The morning following surgery, all subjects will be contacted by phone or in person [if hospitalized] to record lowest, average, highest, and current pain scores; sleep disturbances, and nausea using a 0-10 Likert scale (0 = no nausea; 10 = vomiting). For outpatients, opioid requirements will be recorded while inpatients will have opioid requirements extracted from the electronic medical record. In addition, we will extract antiemetic use from the electronic record. We will collect the times at which subjects felt their block resolve and they consumed their first opioid analgesic pills following recovery room discharge.

Hypothesis 1: Following breast surgery, **analgesia** will be non-inferior in the recovery room with an erector spinae plane block compared with a paravertebral block as measured with the Numeric Rating Scale.

Hypothesis 2: For breast surgery, **opioid** consumption will be non-inferior in the operating and recovery rooms with an erector spinae plane block compared with a paravertebral block (primary: cumulative intravenous morphine equivalents).

Primary end point: In order to claim that erector spinae plane blocks are non-inferior to paravertebral

blocks, both Hypotheses 1 and 2 must be at least non-inferior.

Statistical methods. Descriptive statistics will be provided by arm and in aggregate. Baseline characteristics of arms will be compared using the Wilcoxon-Mann-Whitney and Fisher's Exact tests. Key characteristics that are significantly different (p<0.05) will be included as covariates in the analysis models.

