10. HUMAN SUBJECTS

Inclusion criteria for the trial will be: (1) undergoing unilateral or bilateral breast surgery with at least moderate postoperative pain anticipated; (2) analgesic plan includes a single-injection peripheral nerve block(s); and (3) age 18 years or older.

Exclusion criteria for the trial will be: (1) morbid obesity as defined by a body mass index > 40 (BMI=weight in kg / [height in meters]²); (2) renal insufficiency (preoperative creatinine > 1.5 mg/dL); (3) chronic opioid use (daily use within the 2 weeks prior to surgery and duration of use > 4 weeks); (4) history of opioid abuse; (5) any comorbidity which results in moderate or severe functional

limitation; (6) inability to communicate with the investigators or hospital staff; (7) pregnancy; (8) planned regional analgesic with perineural catheter placement; and (9) incarceration. We will recruit a maximum of 120 subjects. Selection for inclusion will not be based on race or socioeconomic status. The study population of interest includes men and women of all races and socioeconomic status. There will be no participants from vulnerable populations, such as pregnant women, children, or prisoners.

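### Axillary involvement sets the needle levels in both arms and is known before the block, yet it is not a stratification factor; adding it is a cheap improvement

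*Combined protocol and SAP*

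**What the plan says.** All points are from the combined protocol and SAP.

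- **Eligibility (section 10).** Patients qualify if "undergoing unilateral or bilateral breast surgery with at least moderate postoperative pain anticipated". No criterion concerns the axilla. With the block instructions below, this implies that axillary and non-axillary cases are both enrolled.
- **Randomisation (section 9).** Allocation is in "blocks of 4, stratified for unilateral vs. bilateral surgery". Laterality is the only stratifier.
- **Block placement (section 9).** For erector spinae, "this will be at the T3 level for surgery involving the axilla and the T4 level for surgery not involving the axilla". For paravertebral blocks, "For PVBs without axillary work, this will be at the T3 and T5 levels" and "For PVBs with axillary work, this will be at the T2 and T4 levels". Block success is judged "over the approximate level of the ipsilateral 4th thoracic dermatome" in every case.
- **Baseline data (section 9, Preoperative Procedures).** The plan states that "we will collect baseline anthropomorphic information (e.g., age, sex, height, and weight"). These are examples; axillary surgery is not among them.
- **Adjustment (section 9, Statistical methods and Primary aim).** "Key characteristics that are significantly different (p<0.05) will be included as covariates in the analysis models". Which characteristics count as key is not defined. Baseline comparisons use Wilcoxon-Mann-Whitney and Fisher's exact tests. Both primary comparisons pool all subjects, and no estimate by axillary status is described.

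**The concern.** The plan itself treats axillary work as important enough to change where the needle goes in both arms. Such a factor probably also affects pain and opioid use, although the documents do not quantify this. It has to be settled before the block is placed, so it could be used at randomisation at almost no cost.

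As written, balance on it is left to chance. The only correction is a significance test on a baseline table, and that test has little power to flag a moderate imbalance with 50 per arm. A trial that happened to place fewer axillary cases in the erector spinae arm would show a somewhat flattering comparison on both co-primary outcomes. The report would contain nothing by axillary status to help a reader judge it.

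**Working it through.** **Inputs from the plan.** 50 per group; pain margin 1.25, judged on a 95% CI; Fisher's exact test at p<0.05 as the trigger for adjustment; blocks of 4; planning pain distribution with median 3 and quartiles 2 and 5.

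**Inputs assumed.** Axillary share q (40% as the main case, range 20-50%) and added pain from axillary work g (1-2 NRS points). The documents give neither. Axillary status is taken as independent of laterality.

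**1. The plan's own figure.** The stated power for pain is 82%. Put 25% of the probability evenly on scores 0-2, 25% on 3, 25% on 4-5 and 25% on 6-10, and invert the Wilcoxon-Mann-Whitney test at -1.25. With 50 per group the simulated power is 80.7% (10,000 trials). With the top quarter capped at 9 it is 83.1%. Two other readings of the quartile rule give about 88%. The stated figure is reproduced.

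**2. How often the arms differ.** Let A and B be independent Binomial(50, q) axillary counts. The SD of A - B is √(2 × 50 × q(1-q)). At q = 0.4 this is √24 = 4.9 cases. Exact enumeration gives:

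| Share q | Gap ≥5, either direction | Gap ≥8, either direction | Fisher p<0.05 | Gaps ≥5 left unadjusted |
|---|---|---|---|---|
| 20% | 26% | 6% | 2.8% | 89% |
| 30% | 33% | 10% | 3.1% | 91% |
| 40% | 36% | 12.5% | 3.2% | 91% |
| 50% | 37% | 13% | 3.5% | 90% |

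Half of these gaps favour erector spinae: at 40%, 17.9% for 5 or more and 6.3% for 8 or more.

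**3. What the p<0.05 rule lets through.** Around 20 of 50 per arm, 24 against 16 gives p = 0.153 and 25 against 15 gives p = 0.066. Neither triggers adjustment. A gap of 11 (25 against 14) gives p = 0.040.

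**4. Effect on the pain comparison.** Shift in the mean difference = (gap / 50) × g.

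- Gap 5: 5/50 × 1 to 2 = 0.10 to 0.20 points
- Gap 8: 8/50 × 1 to 2 = 0.16 to 0.32 points
- Gap 10: 10/50 × 1 to 2 = 0.20 to 0.40 points

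Against the margin, 0.10/1.25 = 8% and 0.40/1.25 = 32%.

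**5. Type I error.** Take a normal model with within-group SD 2.5, erector spinae worse by exactly 1.25, shares of 30% and 50%, and g of 1 and 2. False non-inferiority over all trials is 0.0245-0.0253, so it stays at 0.025. Among trials where erector spinae has 8 fewer axillary cases, it is about 0.05-0.07.

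**6. After the change.** Blocks of 4 limit the difference within a stratum to 2. Two of the four strata are axillary, so the axillary gap is at most 2 + 2 = 4. The shift is then at most 4/50 × 1 to 2 = 0.08 to 0.16 points.

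**7. Precision of estimates by axillary status.** The 95% CI half-width is about 1.96 × 2.70 × √(2/n), where 2.70 is the SD of the distribution in step 1. With 15 axillary subjects per arm it is 1.93 points; with 25 it is 1.50. Power for non-inferiority at 1.25 in that subgroup alone would be about 33-50%.

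**The case against.** The strongest defence is that randomisation already protects the comparison. There is no bias on average, the overall error rate holds, the plausible shift is small against the margin, and choosing one stratifier for 100 subjects is defensible. All of that stands, and it is why this is an improvement and not a flaw that threatens the trial. The p<0.05 rule is also a safeguard in principle if axillary status counts as key, but it would trigger in only about 3% of trials.

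A reader might infer more from the same passages, and three stronger readings fail.

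- **That the trial is really two different comparisons.** Both arms move up one level together. The erector spinae level lies midway between the two paravertebral levels in each case. Volumes match: 20 mL against 2 × 10 mL unilaterally, and 16 mL against 2 × 8 mL per side bilaterally. Nothing in the documents suggests that the relative effect differs by axillary status.
- **That a pooled pass would hide inferiority in axillary cases.** This needs an assumed deficit confined to those cases. With an assumed 2 points at shares of 20%, 30% and 40%, the pooled pain rule passes in about 53%, 39% and 26% of trials. The average deficit is then 0.4, 0.6 or 0.8 points, inside the margin, and the hypothesis concerns breast surgery as a whole. These rates are for pain only; the opioid test must also pass and might catch some cases. Pooling produces this limitation, and stratifying would not remove it.
- **That the conclusion should be restricted if the axillary estimate crosses the margin.** With a half-width of about 1.5-1.9 points, that estimate is too imprecise to carry such a rule.

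**Conclusion.** The point holds as a cheap, specific improvement. A factor that the plan uses to place the block in both arms is left to chance at randomisation, and the adjustment rule would seldom reach it. At an assumed 40% axillary share, a gap of 5 or more cases arises in about 36% of trials, half of them favouring erector spinae, and about nine in ten of these gaps would stay unadjusted. The plausible cost is 0.1-0.4 NRS points against 1.25, in the affected trials only.

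The size rests on the assumed axillary share and on an assumed 1-2 point effect of axillary work. If that effect is near zero, the imbalance is harmless. The documents do not support a claim of systematic bias, of an inflated overall type I error, or of poorer erector spinae performance in axillary surgery.

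**What to change.** 1. **Section 9, randomisation.** Stratify by laterality and by planned axillary involvement (yes/no), keeping blocks of 4, which gives four strata. Define yes as axillary work planned on any side, so that bilateral surgery with one axilla involved is classified without ambiguity. Record the value before the envelope is opened.
2. **Section 9, Primary aim.** Report the pain and opioid differences with 95% CIs by axillary status, labelled as descriptive, and state that they will be imprecise. Attach no decision rule to them.

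The primary tests and margins need not change.

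**Cost.** Two more sets of sealed envelopes, one recorded field and a few result rows. Smaller strata may end with incomplete blocks, which the cap of 4 already allows for. The cap applies at randomisation; subjects excluded afterwards for a misplaced block could widen the gap in the analysed set.

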4. ESTIMATED DURATION OF THE STUDY

Three years (1 month preparation, 24 months enrollment, 11 months publication prior to closure)

5. LAY LANGUAGE SUMMARY OR SYNOPSIS (no more than one paragraph)

Following painful surgical procedures of the breast, postoperative analgesia is often provided with a paravertebral nerve block (PVB). For intense, but shorter-duration acute pain, a single-injection of local anesthetic is used with a duration of approximately 12 hours. Recently an alternative block has been reported: the erector spinae plane block.² The theoretical benefits include ease of administration since it is a plane superficial to the PVB and therefore easier to identify and target with ultrasound (therefore increasing success rate); and an increased safety margin as there are fewer anatomic structures in the immediate area which could be injured with the needle; and, the target plane is much further from the intrathecal/epidural space relative to the PVB, therefore leakage of cerebrospinal fluid or injury to the spinal cord are less likely with the erector spinae over the PVB. Unfortunately, it remains unknown if the analgesia provided by this new technique is comparable to that provided with the PVB.⁴ We therefore propose to compare these two techniques with a randomized, subject-masked, active-controlled, parallel-arm clinical trial.

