6. SPECIFIC AIMS

The overall objective of the proposed research is to determine the relative risks and benefits of erector spinae plane versus paravertebral blocks for single-injection local anesthetic administration.

Hypothesis 1: Following breast surgery, **analgesia** will be non-inferior in the recovery room with an erector spinae plane block compared with a paravertebral block as measured with the Numeric Rating Scale.

Hypothesis 2: For breast surgery, **opioid** consumption will be non-inferior in the operating and recovery rooms with an erector spinae plane block compared with a paravertebral block (primary: cumulative intravenous morphine equivalents).

Primary end point: In order to claim that erector spinae plane blocks are non-inferior to paravertebral blocks, both Hypotheses 1 and 2 must be at least non-inferior.

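### Randomised subjects whose block fails and is not successfully replaced leave the study, and nothing keeps them in an as-randomised analysis, so both non-inferiority tests are conditioned on a working block

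*Combined protocol and SAP*

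**What the plan says.** Section 9 (Preoperative Procedures) has both block sites viewed with ultrasound. If either is unacceptable, "the subject will not be randomized and will not proceed further with the study". After that, "Subjects will then be randomized using a computer-generated list and opaque, sealed envelopes to" the two arms. The block is then placed and tested: "Single-injection blocks will be considered successful if, within 30 minutes, the subject experiences decreased sensation to cold temperature" near the fourth thoracic dermatome. The next sentence reads: "Misplaced blocks will be replaced successfully, or the patient excluded from further study participation".

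Under Outcome measurements, recovery-room "pain scores, opioid requirements, and antiemetic administration will be recorded by nursing staff masked to treatment group", and "We will collect the times at which subjects felt their block resolve and they consumed their first opioid analgesic pills". Block failure, replacement and the use of another technique are not among the recorded items.

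The statistical methods give the Wilcoxon-Mann-Whitney interval, the margins (1.25 pain points, 2 mg opioid) and a covariate rule. They name no analysis population and give no rule for excluded subjects. The sample size is 50 per arm, with enrolment capped at 120 to allow for dropouts.

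Sections 5 and 7 describe the erector spinae plane as "easier to identify and target with ultrasound (therefore increasing success rate"), and Section 6 sets the overall objective: to "determine the relative risks and benefits of erector spinae plane versus paravertebral blocks". Section 14 lists failed block among the risks of the paravertebral technique.

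**The concern.** The ultrasound screen comes before allocation and does not harm the comparison. The rule on misplaced blocks comes after allocation, and its trigger is a result of the allocated technique. If the two techniques fail persistently at different rates, the arms that remain are no longer the arms that were randomised.

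A difference in failure would then count in neither hypothesis and need not be reported, although the protocol itself raises success rate as a possible advantage of the test block. If erector spinae fails more often, dropping its failures makes non-inferiority too easy to declare. If paravertebral fails more often, a real erector spinae advantage is hidden. Either way the trial would answer whether erector spinae is non-inferior once a block works, whereas Section 6 states the hypotheses for the blocks without that condition.

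**Working it through.** **1. Order of events in Section 9.** Ultrasound screen, randomisation, block, cold test within 30 minutes, replacement or exclusion, surgery, recovery room. The exclusion falls after randomisation and before both primary outcomes. A subject who is successfully re-blocked stays, so only persistent failures are lost. Reading misplaced as failing the cold test is an inference from the adjacent sentences; the text does not define the word.

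**2. Inputs from the plan.** Pain median 3, interquartile range 2 to 5, same in both arms; 50 per arm; non-inferior if the lower 95% limit for paravertebral minus erector spinae exceeds -1.25. Opioid: normal, mean 2.5 mg, SD 2 mg, truncated at 0; margin 2 mg.

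**3. Assumptions, because the documents give no figure.** Pain tails: 25% of the mass spread evenly over each of scores 0-2, 3, 4-5 and 6-10. Unreplaced failure rates as shown below. Each such failure adds 3 pain points, capped at 10. Pain is otherwise equal in the two arms.

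**4. The plan's own figure.** The lower limit is approximately the k-th smallest of the 50 × 50 = 2,500 pairwise differences, with k = 1,250 − 1.96 × √(2,500 × 101/12) ≈ 1,250 − 284 = 966. With no failures, 10,000 simulated trials give 80.9% power, against 82% stated. Other readings of the discrete distribution give 74% to 89%. Monte Carlo error is about √(0.8 × 0.2/10,000) = 0.4 points.

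**5. Mean difference left out.** Scores 8, 9 and 10 (5% each) lose 1, 2 and 3 points to the cap, so the mean effect of a failure is 3 − 0.05 × (1 + 2 + 3) = 2.7. The difference left out is 2.7 × (failure rate in erector spinae − failure rate in paravertebral):

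- 3% and 1%: 2.7 × 0.02 = 0.054, or 4% of the 1.25 margin
- 5% and 1%: 2.7 × 0.04 = 0.108, or 9%
- 10% and 2%: 2.7 × 0.08 = 0.216, or 17%

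Expected subjects lost out of 50 per arm (erector spinae, paravertebral): 1.5 and 0.5; 2.5 and 0.5; 5 and 1.

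**6. Chance of declaring pain non-inferiority, 50 randomised per arm.**

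| Failure, erector spinae / paravertebral | Working blocks only | All randomised |
|---|---|---|
| 2% / 2% | 80.1% | 79.7% |
| 3% / 1% | 80.0% | 77.0% |
| 5% / 1% | 79.6% | 73.8% |
| 5% / 5% | 79.0% | 78.6% |
| 10% / 2% | 78.1% | 65.6% |
| 10% / 2%, half of failures restored by another technique | 78.1% | 73.6% |
| 10% / 2%, all restored | 78.1% | 80.9% |
| 2% / 10% | 78.6% | 87.4% |

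Repeat simulations of the main scenarios with other seeds agreed to within about 2 points. Halving the penalty to 1.5 points gives about 78% against 69% at 10% / 2%, and 80% against 78% at 3% / 1%.

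**7. False positives at a true as-randomised mean deficit of 1.25.** This model already gives 6.3% with no failures, so only the gap within each pair belongs to the exclusion. Working blocks only against all randomised: 7.3% against 6.1% at 3% / 1%; 9.2% against 6.3% at 5% / 1%; 13.3% against 6.8% at 10% / 2%; 2.1% against 5.1% at 2% / 10%.

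**8. Opioid.** With an assumed extra 3 mg per failure (4,000 trials), power is 100% against 99.7% at 10% / 2%. The hypothesis is affected in principle but hardly in size.

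**The case against.** The strongest reply is that the text does not say outcomes are discarded; it says only that the patient leaves the study. That is true. But the patient leaves before either primary outcome exists, and nothing says the outcomes are collected or analysed, so following the plan gives the restricted comparison.

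Second, persistent failures may be rare. Unsuitable sites are screened out, an attending places or directly supervises every block, and replacement is the first option. This stands as a limit on size: at 2% / 2% the gap is 0.4 points, about the Monte Carlo error. The large gaps need a marked excess of erector spinae failures, the opposite of what Sections 5 and 7 suggest. In the direction the protocol expects, the exclusion costs power and hides a benefit; it does not produce a false claim.

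Third, enrolment may go to 120. Refilling to 50 evaluable subjects per arm would hold working-block power at about 80-81%, so the small declines in that column partly reflect not refilling. Refilling does not bring back the excluded subjects, and the 20 extra places must also cover subjects screened out before randomisation and other dropouts.

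Finally, comparing working blocks is a legitimate question in a non-inferiority trial, and alternative analgesia after a failed block can dilute a true difference in the all-randomised analysis. Both points stand. They argue for presenting both analyses with their roles fixed in advance, not for leaving the population undefined.

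**Conclusion.** The concern holds. The plan contains a post-randomisation exclusion that depends on the result of the allocated block, and it has no as-randomised analysis to offset it. That conclusion rests on the text and is firm, subject to reading misplaced as a failed cold test; any other reading would still be a post-randomisation exclusion, with an undefined criterion.

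Confidence in the size is low, because every failure rate, pain penalty and restoration fraction is assumed. In the scenarios examined, the exclusion changes the chance of declaring pain non-inferiority by under 1 point when failures are few and equal, by 3 points at 3% / 1%, by 12.5 points at 10% / 2%, and by 8.8 points the other way at 2% / 10%. If another technique fully restores pain control, only the loss of numbers remains.

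**What to change.** Leave the clinical handling of a failed block as it is and replace the study exclusion with wording such as:

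> *Every randomised subject stays in follow-up, has recovery-room pain scores and operating- and recovery-room opioid use recorded, and is analysed in the randomised arm for both hypotheses, whatever the block result or any later analgesic technique.*

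Add the usual exceptions for withdrawn consent and cancelled surgery. Report the working-block subset as well, and state before data are seen whether it is supportive or must also show non-inferiority; that is the sponsor's choice. Report initial failures, replacements, unreplaced blocks and alternative techniques by arm.

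The cost is protocol and analysis wording plus a record of block result and any alternative technique. Recovery-room pain and opioid use are already recorded, and Hypothesis 2 needs operating-room opioid use anyway. Failed blocks add variance: at 5% / 5%, all-randomised pain power is 78.6% with 50 per arm, against 80.9% with no failures. Randomising 55 per arm gives about 82% but leaves 120 − 110 = 10 places for screened-out subjects and other dropouts. If both analyses must succeed, pain power with 50 per arm is 78.2% at 2% / 2% and 75.9% at 5% / 5%.

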Primary aim. We will test the noninferiority of the erector spinae nerve block compared to the paravertebral nerve block. The 95% confidence interval (CI) associated with the Wilcoxon-Mann-Whitney test will be derived for the group difference (paravertebral minus erector spinae) in median pain scores within the recovery room. If the lower limit of the 95% CI is greater than -1.25, we will conclude noninferiority. If there are significant differences between the groups in any key characteristics, these characteristics will be included as covariates in a linear model. The same noninferiority margin (-1.25) will be applied to the 95% CI for the covariate adjusted group difference in mean pain derived from the linear model.

The noninferiority of the erector spinae nerve block with regard to total opioid consumption within the operating and recovery rooms will be tested in the same manner as pain, i.e. comparing the limits of a 95% CI associated with the Wilcoxon-Mann-Whitney test to a predefined noninferiority margin (in this case 2 mg). Covariate adjusted linear models will again be applied in the event that key characteristics are significantly different between the groups.

Sample size justification. Power for the Wilcoxon-Mann-Whitney derived noninferiority testing is based on 10,000 simulated trials. We simulated pain scores from a discrete distribution with median (interquartile range) 3 (2-5) [Kairaluoma, 2004]. Between the quartiles, the probability of each score was assumed constant. The distribution for each group was assumed to be the same. The sample size of n=50 per group provides 82% power to detect noninferiority in pain with a margin of 1.25. Similarly, opioid consumption was assumed to follow a truncated normal distribution with mean 2.5 mg and standard deviation 2 mg, and minimum value 0 mg. The sample size of n = 50 per group provides at least 95% power to detect noninferiority with margin 2 mg. Therefore, we will enroll 50 subjects for each of two treatments with a total enrollment of 100 subjects. To allow for dropouts, we will request a maximum enrollment of 120 subjects. Noninferiority in pain is tested first, and if significant, noninferiority in opioid consumption is tested. Under this hierarchical testing framework, no adjustment in alpha is necessary to control Type 1 error [Mascha, et al 2012].

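### The next-morning nausea scale runs from no nausea to vomiting and vomiting is recorded nowhere else, so a pooled summary of the score mixes nausea intensity with vomiting

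*Combined protocol and SAP*

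**What the plan says.** Section 9 (Outcome measurements) plans one contact, by phone or in person, on the morning after surgery. Among the items collected is "nausea using a 0-10 Likert scale (0 = no nausea; 10 = vomiting". The plan does not state the period the rating covers. It also does not say how to score severe nausea without vomiting, or vomiting with little nausea.

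The neighbouring items do not record vomiting:

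- In the recovery room, "pain scores, opioid requirements, and antiemetic administration will be recorded by nursing staff masked to treatment group". Neither nausea nor vomiting is listed.
- After that, "In addition, we will extract antiemetic use from the electronic record". This captures treatment, which may be given for either symptom.

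The only analysis statement that reaches the nausea score is general: "Descriptive statistics will be provided by arm and in aggregate". Section 9 gives it no hypothesis, test, margin or sample size, and no rule for handling a score of 10. The primary conclusion rests on recovery-room pain and on opioid use in the operating and recovery rooms: "both Hypotheses 1 and 2 must be at least non-inferior".

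**The concern.** A score between the two anchors is a degree of nausea, while a score at the top is defined by something that happened. Under the stated anchors, a subject who vomited once and then felt well is placed at 10. A subject with severe nausea all night and no vomiting has no anchor that describes the experience. Once the scores are pooled into one summary per arm, a difference between arms may come from more vomiting, worse nausea or both, and a null result may hide opposite movements.

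What is at stake is modest. Section 6 sets the overall objective as to "determine the relative risks and benefits of erector spinae plane versus paravertebral blocks", and nausea is one of the few outcomes collected beyond pain and opioid use. For outpatients this score is the only direct measure of nausea or vomiting specified after discharge, and a record extract may not show antiemetics taken at home. A reader of the results would want to know whether one block led to more vomiting. The score as defined does not reliably answer that.

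**Working it through.** The documents give no figure for nausea or vomiting, so there is nothing to reproduce. Every rate and distribution below is an assumption made to show the mechanism.

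**Step 1: shift in the mean from vomiting alone.** Suppose both arms have the same nausea intensity, every vomiter scores 10, and vomiters would otherwise have rated their nausea *u* on average. An arm with vomiting proportion *v* then has mean score = (mean nausea) + *v* × (10 − *u*). The difference between arms is

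shift = (difference in *v*) × (10 − *u*).

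For an assumed 10 percentage-point difference in vomiting:

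| Assumed *u* | Shift in mean score |
|---|---|
| 3 | 0.10 × 7 = 0.7 |
| 6 | 0.10 × 4 = 0.4 |
| 8 | 0.10 × 2 = 0.2 |
| 9 | 0.10 × 1 = 0.1 |

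The range is 0.1 to 0.7. It is small if vomiters would have rated their nausea near the top anyway.

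**Step 2: whether one summary shows which component moved.** Assume a comparison arm in which 10% vomit (score 10). The non-vomiters score 0 to 9 with percentages 50, 10, 10, 8, 7, 6, 4, 3, 1 and 1, a mean of 1.74. The overall mean is 0.90 × 1.74 + 0.10 × 10 = 2.57. Three alternatives for the other arm are:

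| Case | Vomiting | Mean nausea in non-vomiters | Overall mean | Mean difference | Rank probability |
|---|---|---|---|---|---|
| A: more vomiting only | 20% | 1.74 | 0.80 × 1.74 + 2.00 = 3.39 | +0.83 | 0.55 |
| B: worse nausea only | 10% | 2.66 | 0.90 × 2.66 + 1.00 = 3.39 | +0.83 | 0.60 |
| C: more vomiting, milder nausea | 20% | 0.71 | 0.80 × 0.71 + 2.00 = 2.57 | 0.00 | 0.44 |

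In B, about 46% of the zeros are moved evenly to scores 2 to 6. In C, about 59% of the non-zero scores are moved to 0. The rank probability is the Wilcoxon-Mann-Whitney quantity: the chance that a subject in the altered arm scores higher than one in the comparison arm, plus half the chance of a tie. A value of 0.50 means no difference.

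A and B give the same mean difference from different causes. In C the means are equal and the rank comparison points towards less nausea, although vomiting has doubled. The 0.83 in case A lies outside the range in Step 1 because the extra vomiters are there assumed to have rated only 1.74 otherwise: 0.10 × (10 − 1.74) = 0.83.

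**Step 3: what the share at 10 could recover.** If only vomiters may score 10, the share at 10 is the vomiting proportion and scores 0 to 9 describe nausea in the rest. The plan does not state that restriction, so a subject with extreme nausea and no vomiting may also answer 10. Even with the restriction, the nausea intensity of those who vomited is not recorded. At 50 per group, 10% against 20% vomiting would have about 29% power (two-sided 0.05). The vomiting proportion would therefore be a descriptive result however it is collected.

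**The case against.** The strongest reply is that the two components may be separable after all. If the anchors are followed literally, so that vomiters score 10 and nobody else does, the share at 10 is the vomiting rate. A reader might infer from the mixed anchors that the data can never distinguish vomiting from nausea. The documents do not support that: the mixing is certain only for a pooled summary, and separation fails only so far as 10 is used by subjects who did not vomit. What stands against the plan is that it neither reserves 10 for vomiters nor says the share at 10 will be reported apart from the rest, and that intensity among vomiters is lost either way.

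A second reply is that the plan specifies no comparison of mean nausea scores, so a shift in the mean harms no planned test. This is correct. The unadjusted primary analyses are rank-based, and a rank comparison depends less on how far up the scale vomiters are placed: case A gives only 0.55. But a descriptive table by arm still needs a summary, and cases A to C show that neither a mean nor a rank summary identifies the component that moved.

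A third reply is that a scale from no nausea to vomiting can be read as one combined severity measure, with antiemetic use as a second view. That is a defensible instrument if it is labelled as combined. The plan calls it a nausea scale, and antiemetic use does not count vomiting.

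Finally, nausea appears in no hypothesis in Section 6 and is not among the theoretical advantages listed in Section 7. That limits the importance of the point but does not remove it.

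**Conclusion.** The point holds as a low-cost improvement to a descriptive outcome. Any pooled mean, median or rank summary of the next-morning score combines nausea intensity with vomiting, nausea intensity in subjects who vomited is not captured, and the plan does not make the share scoring 10 a reliable vomiting rate. This follows from the stated anchors and the absence of another vomiting item, and needs no numerical assumption.

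The size does rest on assumptions. The shift of 0.1 to 0.7 points requires an assumed 10 percentage-point difference in vomiting, every vomiter scoring 10, and an assumed alternative rating of 3 to 9. The documents give no vomiting rate or nausea distribution, so the figure is an illustration and not an estimate for this trial.

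A reader might also infer that the flaw weakens the noninferiority claim. It does not: that claim depends only on pain and opioid consumption, and nausea has no role in it.

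**What to change.** In Section 9 (Outcome measurements), add one yes/no question to the contact already planned for the morning after surgery: any vomiting since surgery. Report the proportion who vomited by arm, separately from the nausea score.

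Preferably, also re-anchor the nausea scale so that 10 means worst imaginable nausea. Subjects who vomited then still rate their nausea, and those who did not can use the whole scale. If the existing scale is kept, report the score by vomiting status, using the new item and not the score of 10 to define that status.

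The cost is one question and one extra line on the single-page CRF described in Section 16. Sample size, treatment and the primary analysis do not change. If the scale is re-anchored, scores become less directly comparable with any data collected on the combined scale; keeping the scale and adding only the yes/no item avoids that.
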